5.4.2 Dose-Limiting Toxicity and Determination of Maximum Tolerated Dose

The evaluation period for DLTs will begin on Cycle 1 Day 1 and will continue up to 28 days. All DLTs will be assessed by the investigator using National Cancer Institute Common Terminology Criteria for Adverse Events (NCI CTCAE) v5.0. A DLT will be defined as the occurrence of any toxicity in Table 3, except for events clearly associated with the underlying disease, disease progression, a concomitant medication, or comorbidity.

Individual subject dose reductions may be made based on events observed at any time during treatment with study drug; however, for the purposes of dose cohort escalation/de-escalation, expanding a dose cohort, and determining the MTD/PAD of study drug, decisions will be made based on events that are observed from the first day of study drug administration through and including the 28-day DLT period. A lower MTD may subsequently be determined based on relevant toxicities that become evident after the 28-day DLT period.

Table 3: Definition of Dose-Limiting Toxicity

Nonhematologic toxicity
Any \geq Grade 3 nonhematologic toxicity EXCEPT the following: 
• Transient (\leq 72 hours) abnormal laboratory values without associated clinically significant signs or symptoms.• An event clearly associated with the underlying disease, disease progression, a concomitant medication, or comorbidity.• Asymptomatic changes in amylase and lipase.• Single or non-fasting elevations in blood glucose (i.e., blood glucose excursions will be considered toxicities if fasting blood glucose is elevated on 2 separate occasions). 
Note: Any grade \geq3 non-hematologic toxicity should count as DLTs except those that are clearly and incontrovertibly due to disease progression or extraneous causes.

Hematologic toxicity

• Grade 3 thrombocytopenia with clinically significant bleeding (i.e., requires hospitalization, transfusion of blood products, or other urgent medical intervention).• Grade 4 thrombocytopenia.• \geq Grade 3 febrile neutropenia (absolute neutrophil count $< 1.0 \times 10^9/L$ and fever $> 38.3^{\circ}\text{C}$).• Grade 4 neutropenia that does not recover to \leq Grade 2 in \leq 3 days after interrupting study drug.• Grade 4 anemia not explained by underlying disease or some other concomitant disorder.
Immune-related toxicity

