6 SCHEDULE OF STUDY PROCEDURES

Table 7: Schedule of Assessments (Ph. 1 & Ph. 2)

Visit Day	Protocol Section	Pre-Screening ^c (Phase 1b and Phase 2 ONLY)	Screening (Approx. 30 days prior to C1D1)	Treatment ^a					Post-Treatment ^b			
				All Cycles	Cycles 1 & 5 ^d			Every 8/12 weeks ⁿ	EOT	Safety Follow-Up 1	Safety Follow-Up 2	
				Day 1	Day 2	Day 3	Day 8	Disease Status				
Evaluation/Window (Range)		≥ 7 Days prior to initiation of Screening	~Day - 30 to - 1	± 3 days (after Cycle 1)			± 1 day	± 7 days		30 days (+ 7 days)	90 days (+ 7 days)	
ADMINISTRATIVE PROCEDURES												
Pre-Screening Consent	7.1	X										
Main Informed consent	7.1		X									
I/E criteria	4	X	X									
Demographics	7.2	X	X									
Cancer History and Diagnosis	7.2.2	X	X									
Medical History ^e	7.2		X									
Prior/concomitant meds	7.3						X ^f					
Administer NC762	5.2.1				X							
Post-study anticancer therapy status	7.4									X	X	X
CLINICAL PROCEDURES/ASSESSMENTS												
Comprehensive PE ^g	7.5.2.1		X									
Targeted physical assessment ^f	7.5.2.2			X			X			X		
Vital signs and weight	7.5.3		X	X ^h			X			X		
ECOG performance	7.5.2.1		X	X			X			X		
12-lead ECG ⁱ (Table 12)	7.5.4		X ^j	X ^k						X ^j		
AE assessment	7.5.1						X ^l					
Laboratory assessments ^m (Table 8 and Table 9)	7.5.5		X	X			X			X		
PK/ADA and PD assessments ^m (Table 10 and Table 11)	7.7 and 7.8			X	X ⁿ	X ⁿ	X			X		
Tumor Biopsy ^o	7.8.1	X	X	X						X		
EFFICACY MEASUREMENTS												
Radiologic assessments	7.6.1.1		X ^p					X ^q	X ^r			

a Treatment cycles after Cycle 1 will begin every 14 days (\pm 3 days, after cycle 1). Alternate dosing schedules may also be explored based on emerging data.

b Mandatory safety follow-up should be conducted approximately 30 days and 90 days after EOT visit (or after the last dose of study drug if the EOT visit was not performed). Safety follow-up must be performed before any new systemic anticancer therapy is started regardless of whether it occurs before the end of the 30- or 90-day safety follow-up period. Safety follow-up may be performed by phone.

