c **For Phase 1b and Phase 2 only:** Potential subjects will be consented using short-form ICF prior to pre-screening biopsy to confirm B7-H4⁺ tumor status. Initial review of eligibility criteria will begin and Demographics and Cancer History and Diagnosis must be documented at time of pre-screening. Collection of AEs and Concomitant medications directly related to study procedures will also begin at pre-screening. Subjects confirmed as B7-H4⁺ must be consented a second time, prior to completing the remainder of screening activities for study participation.

d Visit at Day 8 is required for all subjects at Cycles 1 and 5. Visits on Days 2 and 3 are applicable for Phase 1 subjects only.

e Medical history will include relevant medical or surgical treatment within the last 10 years that are considered to be clinically significant by the investigator.

f Any prior medication received up to 30 days before the first dose of study drug and 90 days after the last dose of study drug will be recorded in the eCRF. Please also refer to sections 5.6.2 and 5.6.3 for details on prohibited and restricted medications.

g Comprehensive Physical examinations must be performed by a medically qualified individual such as a licensed physician, physician's assistant, or an advanced registered nurse practitioner, as local law permits. The comprehensive physical examination will include assessment(s) of the following organ or body systems: skin; head, eyes, ears, nose, and throat; thyroid; lungs; cardiovascular system; abdomen (liver, spleen); extremities; and lymph nodes, as well as a brief neurological examination. The screening physical examination should also include a measurement of height. The targeted physical examination will be a symptom-directed evaluation conducted by the investigator or a medically qualified designee. Notable abnormalities that are considered clinically significant in the judgment of the investigator are to be reported as AEs or Medical History (if applicable at Screening).

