h During Cycle 1 subjects will be required to stay at the study site for safety observation for 4 hours post end of infusion. At Cycle 1, vital signs (blood pressure, pulse, respiratory rate, and body temperature) will be collected pre-dose, at end of infusion (+10 minutes), and every 60 minutes (\pm 10 minutes) thereafter. On Day 1 of all subsequent cycles, subjects will be required to be observed for a minimum of 1 hour post end of infusion or per PI discretion if indicated. After cycle 1, vital signs (blood pressure, pulse, respiratory rate, and body temperature) will be assessed pre-dose and at end of infusion (+10 minutes). Subjects will also be assessed for the onset of acute AEs.

i All 12-lead ECGs will be performed with the subject in a recumbent or semirecumbent position after 5 minutes of rest and should not be performed within 15 minutes after a blood collection.

j A single 12-lead ECG should be performed anytime at Screening and EOT.

k ECGs will be performed on Day 1 of Cycles 1 and 5, in conjunction with PK samples at the following timepoints: pre-infusion and post-infusion (+30 minutes). Additional ECGs should be performed per PI discretion if any clinically significant abnormal findings are noted or as indicated.

l AEs will be collected after ICF has been signed and through end of study. The severity of AEs will be assessed using NCI CTCAE v5.0 Grades 1 through 4. The NCI CTCAE v5.0 severity of Grade 5 will not be used;

m If a central line is used for study drug infusion, collect blood samples via peripheral blood draw to prevent sample contamination.

n Visit/lab assessments on Day 2 and 3 are required for Phase 1 subjects only.

o For Phase 1a, tumor biopsies are optional. Biopsies are required for all Phase 1b and Phase 2 subjects. Biopsies will be collected at Pre-Screening (Phase 1b and Phase 2 only), Screening (Phase 1 subjects), and at Cycle 3 (prior to Cycle 4 dose). An optional EOT biopsy will be collected for subjects who consent for EOT biopsy at time of ICF.

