p The initial tumor imaging will be performed within 30 days before the first dose of study drug. Scans performed as part of routine clinical management are acceptable for use as the screening scan if they are of diagnostic quality and performed within 30 days before the first dose of study drug. The same imaging technique should be used for a subject throughout the study. Local reading (investigator assessment with site radiology reading) will be used to determine eligibility and for subject management.

q On-study imaging will be performed at Week 8 (during Cycle 4), then every 8 weeks (56 days \pm 7 days) for the first 6 months, and then every 12 weeks (84 days \pm 7 days) thereafter. Imaging should follow calendar days and should NOT be adjusted for delays in cycle starts. If imaging shows disease progression, then another imaging assessment should be performed 4 to 6 weeks later to confirm progression per mRECIST.

r If scan was obtained within 4 weeks prior to the date of discontinuation, then a scan at treatment discontinuation (EOT) is not mandatory. For subjects who discontinue study therapy without confirmed disease progression, a radiologic evaluation should be repeated at the time of treatment discontinuation (i.e., date of discontinuation \pm 4-week window). For subjects who discontinue treatment for reasons other than disease progression, every effort should be made to continue monitoring their disease status every 8 weeks (56 days \pm 7 days) for the first 6 months (from first dose) and then every 12 weeks (84 days \pm 7 days) by radiographic imaging until 1) withdrawal of consent, 2) the start of new systemic anticancer therapy, 3) documented disease progression, 4) death, or 5) the end of the study, whichever occurs first.

Table 8: Schedule of Local Laboratory Assessments (Ph. 1 & Ph. 2)

Visit Day	Protocol Section	Screening ^a	Treatment			Post-Treatment EOT
			C1 and C5		Day 1 of All Other Cycles	
			D1 ^a	D8	D1 ^c	
Evaluation/Window (Range)		~Day - 30 to - 1	Pre-infusion ^{b,c}	± 1 day	- 3 days	
Comprehensive serum chemistries ^d	7.5.5	X	X	X	X	X
Hematology with differential ^e	7.5.5	X	X	X	X	X
Coagulation panel ^f	7.5.5	X	X	X	X	X
Urinalysis ^g	7.5.5	X	X	X	X	X
Endocrine function tests ^h	7.5.5	X	X	X	X	X
Hepatitis B and C ⁱ	7.5.5.2	X				
Serum pregnancy test (childbearing females only) ^j	7.5.5.1	X ^j				X
Urine pregnancy test (childbearing females only) ^k	7.5.5.1		X ^l		X ^l	

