6.2 Treatment

The treatment period begins on the day the subject receives the first dose of study drug (Cycle 1 Day 1) through the point at which the investigator determines that the subject will be permanently discontinued from study drug. Cycle 1 Day 1 must occur within approximately 30 days after the subject has signed the main ICF.

Subjects will have regularly scheduled study visits on Day 1 of every cycle \pm 3 days (after Cycle 1). Additional visits will be required on Day 2 and 3 (for subjects enrolled in Phase 1 only) and at Day 8 (all subjects) of Cycles 1 and 5. During study visits, the subject will have clinical and laboratory assessments as outlined in Table 7 and Table 8. At certain study visits as indicated in [Section 7.7](#) and [Section 7.8](#), subjects will have PK, PD, and biomarker samples obtained (see Table 10 and Table 11). Toxicities will be monitored continuously and will be graded using the NCI CTCAE v5.0 criteria.

During Cycle 1 subjects will be required to stay at the study site for safety observation for 4 hours post end of infusion. At Cycle 1, vital signs (blood pressure, pulse, respiratory rate, and body temperature) will be collected pre-dose, at end of infusion (+10 minutes), and every 60 minutes (\pm 10 minutes) thereafter. On Day 1 of all subsequent cycles subjects will be required to be observed for a minimum of 1 hour post end of infusion or per PI

discretion if indicated. After cycle 1, vital signs (blood pressure, pulse, respiratory rate, and body temperature) will be assessed pre-dose and at end of infusion (+10 minutes).

It is recommended that the subject does not leave the site for any reason during the safety observation period. During the safety observation period, subjects will be assessed for the onset of acute AEs.

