7.5.5 Laboratory Assessments

A laboratory local to the study site and subject will perform all clinical laboratory assessments for safety (i.e., blood chemistries, hematology assessments, coagulation tests, endocrine function, and urinalysis). The investigative site will enter the laboratory results into the eCRF and select the laboratory name so that the laboratory normal ranges will populate. All local laboratory assessments should be performed using standard procedures on the days indicated in Table 7 and Table 8. Table 9 lists the specific laboratory analytes required for each test. Additional testing may be required by the sponsor based on emerging safety data. Additional tests may also be performed if clinically indicated.

Serum chemistry, hematology, coagulation, urinalysis, and endocrine function tests must be performed during screening period and on Cycle 1 Day 1.

Laboratory samples collected on Cycle 1 Day 1 must be performed before study drug administration. Cycle 1 Day 1 safety lab results should be reviewed by the investigator or qualified designee and found to be acceptable prior to study drug administration.

After Cycle 1, pre-infusion laboratory procedures can be conducted up to 72 hours before study drug administration, and results should be reviewed by the investigator or qualified designee and found to be acceptable before a new cycle of treatment is initiated.

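### Phase 1 requires no safety laboratory panel between dose 2 and Day 28, so a symptom-free laboratory DLT after dose 2 can be scored as no DLT

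*Combined protocol and SAP*

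**What the plan says.** Section 5.4.2 sets the window: "The evaluation period for DLTs will begin on Cycle 1 Day 1 and will continue up to 28 days". It bases cohort escalation, cohort expansion and the MTD/PAD on events observed in that period, and adds that a lower MTD may be set later on toxicities that emerge afterwards.

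Table 7, footnote a, sets the dosing calendar: "Treatment cycles after Cycle 1 will begin every 14 days", with a visit window of plus or minus 3 days after Cycle 1. Footnote d limits mid-cycle visits: "Visit at Day 8 is required for all subjects at Cycles 1 and 5". Section 6.2 repeats this: "at Day 8 (all subjects) of Cycles 1 and 5". The Day 2 and Day 3 visits belong to the same two cycles (footnote n: "Visit/lab assessments on Day 2 and 3 are required for Phase 1 subjects only") and have no column in Table 8.

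Table 8 schedules safety panels on Days 1 and 8 of Cycles 1 and 5. The remaining cycles share one column, "Day 1 of All Other Cycles", with a window of minus 3 days. Section 7.5.5 gives the same allowance: "After Cycle 1, pre-infusion laboratory procedures can be conducted up to 72 hours before study drug administration".

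Table 3 includes DLTs that are laboratory values. Examples are "Grade 4 thrombocytopenia" with no minimum duration, Grade 4 neutropenia without timely recovery, Grade 4 anemia, and combined ALT and bilirubin elevation. Section 9.2.1 defines a DLT-evaluable subject by a full dose and 28 days of follow-up. It does not ask for a laboratory result after dose 2.

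**The concern.** The window covers two doses, but the laboratory schedule is dense only after the first. After dose 2, a subject who feels well may have no blood count or liver panel until the visit for dose 3. The 3+3 rule and the Phase 1b rule (fewer than 3 of 10 with a DLT) cannot tell a subject who was measured and normal from one who was not measured. Both count as DLT-free. Missed events can only lower the observed DLT count, so the error favours escalation and a higher MTD, which is a primary objective of a first-in-human trial.

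The second fortnight may also be the period of higher exposure. Section 1.2.1 reports a monkey terminal half-life of about 10 days. If the human value were similar (an assumption), exposure after dose 2 relative to dose 1 would be about 1 + 0.5^(14/10) = 1.38.

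**Working it through.** The plan gives no figure on this point to reproduce. The check is a calendar, followed by two illustrations.

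**Calendar.** Day 1 of cycle k is study day 1 + 14(k - 1), so Cycles 1, 2 and 3 start on Days 1, 15 and 29. Adding Cycle 1 Day 8, the nominal panel days are 1, 8, 15 and 29, with gaps of 7, 7 and 14 days. The Day 15 panel precedes dose 2. No nominal panel falls on Days 16-28, which is 13 of the 28 window days.

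**Allowed windows.** For a Day 29 visit the Cycle 3 panel may be drawn on Days 26-29. If the visit itself moves by up to 3 days either way, the range is Days 23-32. A draw inside the window is therefore allowed but not guaranteed.

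**Illustration 1: detection.** Assume an abnormality lasts L days with onset equally likely on each of Days 16-28 (13 days).

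- One draw on Day 29 sees onsets from Day 30 - L onward, so (L - 1)/13 are seen and (14 - L)/13 are never sampled.
- One draw on Day 26, 27 or 28 sees L/13 for the durations shown, all inside the window.

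| Duration L | Never sampled, Day 29 draw | Seen on Day 29 | Seen in window, one draw on Days 26-28 |
|---|---|---|---|
| 4 days | 10/13 = 77% | 3/13 = 23% | 4/13 = 31% |
| 7 days | 7/13 = 54% | 6/13 = 46% | 7/13 = 54% |
| 10 days | 4/13 = 31% | 9/13 = 69% | 10/13 = 77% |

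Treating onset as continuous over the 14 days after dose 2 gives 71%, 50% and 29% never sampled, so the picture does not depend on the day grid. For 7-day episodes, adding a Day 22 panel captures 13/13 with a Day 28 draw, 12/13 = 92% with Day 27 and 11/13 = 85% with Day 26.

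**Illustration 2: decisions.** Let p be the true DLT probability and f the share of all DLTs missed, so the observed probability is q = p(1 - f). The 3+3 rule escalates with probability (1 - q)^3 + 3q(1 - q)^5. The Phase 1b rule deems a cohort safe with probability P(X ≤ 2), X ~ Binomial(10, q).

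| Rule, true p | All seen | f = 10% | f = 25% | f = 50% |
|---|---|---|---|---|
| 3+3, 0.20 | 71% | 75% | 81% | 91% |
| 3+3, 0.33 | 43% | 50% | 61% | 78% |
| 3+3, 0.40 | 31% | 38% | 49% | 71% |
| Phase 1b, 0.20 | 68% | 74% | 82% | 93% |
| Phase 1b, 0.33 | 31% | 39% | 53% | 78% |
| Phase 1b, 0.40 | 17% | 24% | 38% | 68% |

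For p = 0.33 and f = 0: 0.67^3 + 3(0.33)(0.67^5) = 0.301 + 0.134 = 0.434.

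The documents give neither L nor f.

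**The case against.** Several points on the other side stand.

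- **The window can contain a sample.** A reader might infer that nothing after dose 2 can be seen in time. The 3-day and 72-hour allowances rule that out: a Day 26-28 draw complies with the plan.
- **Day counting is unsettled.** A Day 29 pre-dose sample comes 28 elapsed days after dose 1. The text does not say whether it is inside the window.
- **Later findings are not ignored.** A reader might infer that the MTD rests on Day 28 data alone. Section 5.4.2 allows a lower MTD afterwards, and Sections 5.4.5 and 8.7 have investigators review overall safety data.
- **Only silent events are exposed.** Symptomatic events reach the record through AE reporting and unscheduled tests. Non-hematologic laboratory changes of 72 hours or less without clinically significant signs or symptoms are not DLTs.
- **The monkey neutropenia is weak support.** It occurred in 1 of 10 animals at 100 mg/kg, five times the top planned dose, and Section 1.2.3 calls its relation to drug uncertain. Low counts were recorded from study day 31 to 55, a span of 24 days. An episode that long starting on Days 16-28 would still be present on Day 29. The case shows that a low count can occur without illness; it does not show that short episodes fall in this gap.

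None of this requires a sample. Testing on clinical indication needs a trigger, the later MTD revision is discretionary, and neither recovers an episode that resolved unmeasured.

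**Conclusion.** The gap is real and follows from the schedule itself. A site can follow the plan exactly and a subject can be scored DLT-free with no safety panel after dose 2 inside the window. The direction of the bias, toward escalation, is certain; its size is not known. The 54% figure rests on 7-day episodes, even onset over Days 16-28 and a Day 29 draw. The rise from 43% to 50-78% rests on a true rate of 33% and a missed share of 10-50% of all DLTs. A reader might take these as forecasts for NC762, but the documents give no missed share. The day numbers hold for the starting 14-day schedule and would shift under an alternate one. This is an inexpensive correction worth making, not evidence that the escalation design fails.

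**What to change.** For Phase 1, reconcile Table 8 with the DLT window in Section 5.4.2 and the evaluability definition in Section 9.2.1:

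1. Make the Cycle 3 Day 1 pre-infusion panel part of the DLT assessment. Either draw it within the existing 3-day allowance so that it falls by the end of the window, or state that the sample before dose 3 counts as inside the window.
2. Count its findings in the DLT decision.
3. Do not close a subject's DLT review, or count the subject as DLT-free, until the panel is available.

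The cost is small but not nil. A Day 26-28 draw before a Day 29 infusion can mean a separate local attendance. If the Cycle 3 visit slips to Day 32, a Day 28 sample is more than 72 hours before dosing and the panel must be repeated. Review may wait a day or so for results. Counting the Day 29 sample avoids the extra attendance and gives up little: 46% against 54% of 7-day episodes in Illustration 1.

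A Cycle 2 Day 8 panel (Day 22) would close most of what remains. It is optional and adds one local draw for each of up to about 50 Phase 1 subjects (30 + 20). Additional sampling in Cycle 1 would not help, since the gap lies after dose 2.

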6.1 Screening

Screening is the interval between signing the ICF and the day the subject is enrolled in the study (e.g., Cycle 1 Day 1).

Note: During Phase 1b and Phase 2, potential subjects will be consented first using short-form ICF prior to pre-screening biopsy to evaluate for B7-H4+. Confirmed B7-H4+ subjects must be consented a second time using the main ICF, prior to completing remainder of screening activities for study participation.

Screening assessments should be completed within a period of approximately 30 days. Informed consent must be obtained before performing any study-specific procedures that are not considered standard of care. However, procedures conducted as part of the subject's routine clinical management obtained before signing of informed consent may be used for screening or baseline purposes with approval of the medical monitor, provided that the procedure meets the protocol-defined criteria. Assessments that are required to demonstrate eligibility may be performed over the course of one or more days during the screening process.

Results from the screening visit evaluations will be reviewed to confirm subject eligibility before enrollment or administration of study drug. Tests with results that fail eligibility requirements may be repeated **once** during screening if the investigator believes the results to be in error. For screening assessments that are repeated, the most recent available result before enrollment will be used to determine subject eligibility. Additionally, a subject who fails screening may repeat the screening process **1 time** if the investigator believes there has been a change in eligibility status (e.g., after recovery from an infection). Treatment should start as soon as possible after the date of enrollment.

